### **Reporting schedule:**

- All adverse events that are serious (SAE) and unexpected (i.e., have not been previously reported for the study's intervention) will be reported to the IMPACT Collaboratory Regulatory and Data Team Leader ([name]), NIA IMPACT Collaboratory PO ([name]), and the IMPACT Collaboratory Safety Officer within 48 hours of the study's knowledge of SAE.
- Only those adverse events that are serious (SAE), unexpected, and related to the intervention must also be reported to Advarra IRB. Unexpected and unrelated SAEs will be reported to Advarra IRB on a case-by-case basis if requested by the IMPACT Collaboratory Safety Officer or NIA IMPACT Collaboratory PO.
- All deaths will be reported to IMPACT Collaboratory Regulatory and Data Team Leader ([name]), NIA IMPACT Collaboratory PO ([name]), and the IMPACT Collaboratory Safety Officer within 24 hours of study's knowledge of death.
- Advarra IRB does not require the specific reporting of death outside of the SAE reporting requirement above, but they will be notified on a case-by-case basis if requested by the IMPACT Collaboratory Safety Officer or NIA IMPACT Collaboratory PO.
- All unanticipated problems (UPs) will be reported to the IMPACT Collaboratory Regulatory and Data Team Leader ([name]), Advarra IRB, NIA IMPACT Collaboratory PO ([name]), and the IMPACT Collaboratory Safety Officer within 48 hours of the study's knowledge of the event.
- The summaries of all previously reported unexpected and related SAEs, deaths, and UPs, as well as all other SAEs and AEs will be reported to IMPACT Collaboratory Regulatory and Data Team Lead ([name]), Advarra IRB, NIA IMPACT Collaboratory PO ([name]), and the IMPACT Collaboratory Safety Officer at a minimum every 6 months, or at a frequency requested by the IMPACT Collaboratory Safety Officer or NIA IMPACT Collaboratory PO.

#### **7.3.1 Reporting Procedures**

All data and safety monitoring reporting will classify SAEs and AEs as to their severity, expectedness, and potential relatedness to the study intervention as per the definitions below:

##### **Severity**

- **Mild:** Awareness of signs or symptoms, but easily tolerated and are of minor irritant type causing no loss of time from normal activities. Symptoms do not require therapy or a medical evaluation; signs and symptoms are transient.
- **Moderate:** Events introduce a low level of inconvenience or concern to the participant and may interfere with daily activities, but are usually improved by simple therapeutic measures; moderate experiences may cause some interference with functioning
- **Severe:** Events interrupt the participant's normal daily activities and generally require systemic drug therapy or other treatment; they are usually incapacitating

### Expectedness

- **Unexpected** - nature or severity of the event is not consistent with information about the condition under study or intervention in the protocol, consent form, product brochure, or investigator brochure.
- **Expected** - event is known to be associated with the intervention or condition under study.

### Relatedness

- **Definitely Related:** The adverse event is clearly related to the investigational agent/procedure – i.e. an event that follows a reasonable temporal sequence from administration of the study intervention, follows a known or expected response pattern to the suspected intervention, that is confirmed by improvement on stopping and reappearance of the event on repeated exposure and that could not be reasonably explained by the known characteristics of the subject's clinical state.
- **Possibly Related:** An adverse event that follows a reasonable temporal sequence from administration of the study intervention follows a known or expected response pattern to the suspected intervention, but that could readily have been produced by a number of other factors.
- **Not Related:** The adverse event is clearly not related to the investigational agent/procedure - i.e. another cause of the event is most plausible; and/or a clinically plausible temporal sequence is inconsistent with the onset of the event and the study intervention and/or a causal relationship is considered biologically implausible.

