### **7.3 Adverse Events and Serious Adverse Events**

**AE Definition:** AE is any untoward or unfavorable medical occurrence in a human study participant, including any abnormal sign (e.g. abnormal physical exam or laboratory finding), symptom, or disease, temporally associated with the participants' involvement in the research, whether or not considered related to participation in the research.

**SAE Definition:** SAEs consist of any adverse event that results in death; is life threatening or places the participant at immediate risk of death from the event as it occurred; requires or prolongs hospitalization; causes persistent or significant disability or incapacity; results in congenital anomalies or birth defects; is another condition which investigators judge to represent significant hazards.

**Unanticipated Problem (UP) Definition:** any incident, experience, or outcome that meets all the following criteria:

- unexpected, in terms of nature, severity, or frequency, given (a) the research procedures that are described in the protocol-related documents, such as the IRB-approved research protocol and informed consent document; and (b) the characteristics of the study population;
- related or possibly related to participation in the research;
- suggests that the research places participants or others at a greater risk of harm (including physical, psychological, economic, or social harm) than was previously known or recognized.

**AEs for this study include:** No AEs are expected. More than 150 CPs have completed the MBDC program with no reports of adverse events. There is a small potential for increased stress as a part of participation in the MBDC program.

**SAEs for this study include:** No SAE are expected. More than 150 CPs have completed the MBDC program with no reports of adverse events.

**Process for identifying AEs, SAEs, and UPs:** AEs, SAEs and UPs related to participation in the MBDC program will be collected by the instructors and entered into the Presence Care website database (REDCap system) where CP participation, such as attendance is collected. Entry of AEs, SAEs, and UPs will trigger an alert to the PI who will evaluate (and investigate if necessary), then categorize its severity, expectedness, and potential relatedness.

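### Under the section 7.3.1 definitions a serious harm of a new kind cannot be classed as related, so read literally it misses mandatory individual IRB reporting

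*Combined protocol and SAP*

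**What the plan says.** Section 7.3.1 says that safety reporting will "classify SAEs and AEs as to their severity, expectedness, and potential relatedness to the study intervention as per the definitions below". There are three relatedness categories.

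- **Definitely Related**: among other conditions, the event "follows a known or expected response pattern to the suspected intervention, that is confirmed by improvement on stopping and reappearance of the event" when exposure is repeated.
- **Possibly Related**: the timing is reasonable and the event "follows a known or expected response pattern to the suspected intervention, but that could readily have been produced by a number of other factors", so the same pattern condition applies.
- **Not Related**: the event is clearly unrelated, because "another cause of the event is most plausible", or because the timing does not fit or a causal link is biologically implausible.

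Under Expectedness in the same section, an event is unexpected when its "nature or severity of the event is not consistent with information about the condition under study or intervention in the protocol" or in the other listed study documents. The reporting schedule in section 7.3 adds its own gloss: an unexpected event is one not reported before for the intervention.

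The schedule then sets the IRB trigger: "Only those adverse events that are serious (SAE), unexpected, and related to the intervention must also be reported to Advarra IRB". On what is already known about harms, section 7.3 states: "More than 150 CPs have completed the MBDC program with no reports of adverse events".

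**The concern.** Individual IRB reporting of an SAE exists mainly to catch serious harm that nobody foresaw and that the intervention may have caused. Here the two halves of the trigger pull against each other. To be unexpected, an event must depart from what is known. To be related, it must match what is known. For an intervention with no recorded adverse events, little is on file for a new event to match.

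The study also asks for a waiver of informed consent for all its aspects, and section 11.2 supports that request with minimal risk and the absence of reported adverse events. The IRB therefore has good reason to want prompt notice of anything that changes that picture.

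**Working it through.** No figure is involved, so the check is to run types of event through the definitions, treating each list of conditions as joined by AND.

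**1. A serious event new in nature, with plausible timing and no better explanation.**
- Expectedness: unexpected, both under section 7.3.1 and under the gloss in the reporting schedule.
- Definitely Related: fails, because there is no recognised pattern of response for it to follow.
- Possibly Related: fails for the same reason.
- Not Related: also fails. No other cause is more plausible, the timing fits, and nothing makes a causal link implausible.
- Result: the event falls in no category. There is no unknown or unlikely category and no default rule. The IRB trigger needs serious AND unexpected AND related; the third condition is not met.

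**2. A serious event of the stress, anxiety or depression type.**
- Pattern: section 7.3 names increased stress; section 7.2 names concerning stress or anxiety, to be recorded as an AE; section 7.1 treats a pre- to post-course rise in depressive symptoms or burden as possible harm from the course. Such an event can follow an anticipated pattern.
- Expectedness: under the schedule's gloss it is unexpected, since no adverse events have been reported. Under section 7.3.1 it can be unexpected through its severity.
- Result: it can be unexpected and Possibly Related together. It meets the IRB trigger, provided that related includes Possibly Related, which the schedule does not say.

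**3. The unanticipated problem (UP) route for the event in step 1.** The UP definition in section 7.3 asks for an unexpected event that is related or possibly related to taking part in the research and that suggests greater risk. It does not refer to section 7.3.1, whose introduction mentions only SAEs and AEs. If the investigator borrows those definitions, the only ones the protocol gives, the event fails the second criterion. On the ordinary meaning of the words it passes, and goes to the IRB within 48 hours.

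**4. What reaches whom regardless of relatedness.** From the reporting schedule:
- Serious and unexpected events go to the Collaboratory lead, the NIA program officer and the Safety Officer within 48 hours.
- Deaths go to the same three within 24 hours.
- Unexpected SAEs judged unrelated go to the IRB if the Safety Officer or the NIA program officer asks.
- All other SAEs and AEs go to the IRB in a summary at least every 6 months.

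So for the event in step 1 the route that closes is mandatory individual IRB reporting, and the UP route closes only on one of its two readings.

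**The case against.** The best case for leaving the text alone is that the harm would not go unseen. The people who can call for an IRB report are told within 48 hours whatever the relatedness, and the IRB has its periodic summary. The pattern phrase is not tied to any list, so a sensible investigator could read it generously. All of this stands, and it limits the consequence. It does not supply a category for the event, and it replaces a mandatory report with one that depends on a request or on the summary cycle.

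A reader might infer several stronger things that the documents do not support.

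- *That a new harm would never reach the IRB unless someone asked.* The summary sent at least every 6 months has no relatedness condition.
- *That only unusually severe stress reactions could ever be reportable.* Sections 7.1 and 7.2 also point to anxiety, depressive symptoms and burden, and under the schedule's gloss any such serious event is unexpected without being unusually severe.
- *That UP reporting is closed as well.* That holds only if the section 7.3.1 definitions are carried over to UPs.
- *That Definitely Related is impossible because it must be "confirmed by improvement on stopping and reappearance of the event on repeated exposure" and previous MBDC participants are excluded.* The classes are weekly, so a participant can miss sessions and return, and recurrence can be seen within one course. The exclusion criterion does not prevent that.
- *That the investigator would be forced to choose Not Related.* That category is for events that are clearly unrelated; the text pushes an uncertain event nowhere.

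**Conclusion.** The concern holds in a limited form. As written, a serious harm new in nature, with plausible timing and no better explanation, has no relatedness category and cannot meet the trigger for mandatory individual IRB reporting. Stress-, anxiety- and depression-type events can.

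The size is one reporting route, plus the 48-hour UP route on one reading. Notice to the Safety Officer and the NIA, and the IRB's periodic summary, are unaffected. The documents give no SAE rate, so the number of events affected among up to 130 participants cannot be calculated; the protocol expects none.

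The conclusion assumes that the definitions are applied literally, as section 7.3.1 directs for SAEs and AEs. The reassurance from the other routes assumes that the event is recorded at all. Section 7.3 describes collection by instructors in terms of events related to taking part in the program, so that assumption is not automatic. The change is worth making because the excluded kind of event is the one that expedited IRB reporting is there to catch.

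**What to change.** 1. In section 7.3.1, remove the pattern condition from Possibly Related, so that the category covers an event with plausible timing for which a contribution of the intervention cannot be ruled out.
2. In the same place, state that any event that is neither Definitely Related nor Not Related is classed as Possibly Related.
3. In the reporting schedule in section 7.3, state that related means Definitely or Possibly Related. This brings the IRB trigger into line with the UP definition, which already includes possibly related events.

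Definitely Related can stay as it is, because the default in step 2 catches any event that falls short of it. The cost is a few sentences of wording and slightly more individual IRB reports, since some events that now fit no category would become Possibly Related.

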#### 7.3.2 Follow-up for Adverse Events

The occurrence of an adverse event (AE) or serious adverse event (SAE) may come to the attention of the instructor during MBDC program classes. Instructors will capture these events in the REDCap database and follow-up as needed with CP participants.

## **7.4 Safety Monitoring**

A NIA-appointed Data and Safety Monitoring Officer will monitor this study.

## **8 INTERVENTION DISCONTINUATION**

MBDC instructors may recommend a CP discontinue the program if participants are unable to meet the time commitment or have had a change in caregiving status. Care partners may withdraw voluntarily from participation in the study at any time and for any reason. There will be no replacement of subjects who discontinue early in this pilot study.

## **9 STATISTICAL CONSIDERATIONS**

### **9.1 General Design Issues**

#### **Design choice and rationale**

A stepped wedge trial design was chosen to ensure all participants had the opportunity to participate in the MBDC course. This trial design has each individual contribute control and intervention data, allowing for within participant comparisons. The stepped wedge trials also provides flexibility with rolling recruitment as opposed to the requirement to fill a class that starts on a particular date, which has been a barrier in other mindfulness trials. An adaptive randomization schematic was chosen to ensure that the classes fill up at a relatively similar rate, another pragmatic concern to consider before attempting a larger study. For the secondary aim, shorter versions of the validated scales used to assess efficacy were chosen to align with the pragmatic nature of this work, ensuring participants spend minimum amount of time possible providing clinical outcome data.

#### **Hypotheses and Outcomes**

This pilot study will determine if it is feasible to implement the MBDC program with fidelity for testing in a full-scale ePCT. The primary feasibility progression criteria will be assessed using the previously described measures of feasibility, acceptability, and fidelity. For the progression criteria to be met with no modifications, we will require >75% participants attend (or watch video makeup) for at least 6 of 9 sessions. If that number is between 50% and 75%, we would recommend the study progress, however we will make modifications to increase adherence. We also define progression criteria based on the diversity of recruitment within the pilot. If our participants are not representative of the PWLD population's racial and ethnic demographics within each care system, we will recommend changes to the recruitment strategy to encourage a higher enrollment rate of CPs who represent these populations. If progression criteria are met, secondary feasibility measures including the completeness of the clinical outcomes will be used to help direct data collection approach in future trials.

The efficacy hypothesis is that participation in the MBDC course programming will reduce depressive symptoms and burden while increasing self-compassion and mindfulness in CPs for PLWD. These outcomes will be measured using the following assessments:

### **Clinical Outcome Scales for Efficacy:**

Center for Epidemiologic Studies Depression Scale (CES-D): The Center for Epidemiologic Studies Depression Scale measures self-reported symptoms associated with depression. It has been validated for dementia and multiple other diagnoses, and it is sensitive to differences between caregivers and non-caregivers. The 10-item version has been shown to retain the reliability and validity of the original 20-item scale in the elderly population.

Zarit Burden Inventory: The Zarit Burden Inventory is an interview that evaluates caregiver burden through a self-report measure. The survey scores are positively correlated with behavior problems in older adults and depression scores of caregivers. The shortened version of this scale, the ZBI-6, demonstrated comparable discriminative and internal consistency as the original 12-item versions.

### **Clinical Outcomes for Behavior Change**

The State Self-Compassion Scale Short Form: To evaluate self-compassion, participants indicated how often they acted in the manner stated in each of the items on a scale of 1 (almost never) to 5 (almost always). The survey evaluates self-kindness versus self-judgement, common humanity versus isolation, and mindfulness versus over-identification.

Mindful Attention Awareness Scale: This 5-item scale asks participants to indicate at what level they relate to specific experiences, aimed at measuring main characteristics of mindfulness. Higher scores represented elevated levels of mindfulness expression.

## **9.2 Sample Size and Randomization**

**Sample size rationale:** The sample size is largely determined by the logistics of the pilot award funding and time period. We plan to enroll up to 130 in MBDC courses offered during the study timeframe (up to 15 CP/course). While this pilot is not formally powered for efficacy, we estimate that a sample size of 120 would allow detection of a 3-point change in CES-D-10 scores associated with the intervention, assuming a modest correlation of scores within course session (ICC = .10) and CES-D-10 score standard deviation of 4, with 80% power and a two-sided alpha of 0.05. The results from the pilot will be used to better inform power-calculations for a large ePCT specifically to provide an estimate of the ICC associated with course cluster as this parameter is key in determining a study's power a-priori. Table 2 provides estimates of the current study's expected effect size with a range of assumptions for ICC value (0 to 0.3) and average CES-D-10 scores for the control period (10 to 15), as well as estimates for a hypothetical ePCT with a sample size of 450 (30 courses, 15 per course) maintaining at least 80% power.

**Table 2A.** Effect size estimates for pilot study and full ePCT with varying ICC

ICC	Effect Size: Difference in CES-D-10 change between control and intervention	
	Pilot Study N = 120, Courses = 8	Large ePCT N = 450, Courses = 30
0	2.68	1.32
0.1	2.99	1.49
0.3	2.86	1.44

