**Table 3.**

	Counts for feasibility	Use in analysis
Participants contacted	N	Total number of targeted mailings Estimate of clinic flyer distribution using print rates
Participants who enroll and are randomized into MBDC course section	a	Recruitment rate: a/N
Participants who start MBDC course	b	Participation rate: b/N, compare to a/N
Participants who complete course (6/9 modules)	c	Completion rate: c/b, used as main progression criteria Overall successful enrollment rate: c/N
Number who complete each module in real-time – k = 1, ..., 9	d k	Module specific completion rate: d k /b

Number who complete each module as a make-up session – k = 1, ..., 9	$e_k$	Module specific make-up completion rate: $e_k/b$ Compare to $d_k/b$ to assess fidelity of make-up offerings
Number who complete each questionnaire – m = 1,2,3	$f_m$	Questionnaire specific response rate: $f_m/a$ and/or $f_m/b$ if $a \neq b$

**Aim 2 - Secondary Feasibility and Efficacy Analyses:** The completeness of the CED-D-10 and ZBI-6 outcomes will be quantified by calculating the rate of CPs that respond to all items on each scale (CES-D-10: 10 items, ZBI-6: 6 items) at each assessment. The rate of completion for both scales will be presented overall and stratified by questionnaire, site, and by CP demographics. As the current study design results in a non-uniform length of the control period, the weeks between Q1 and Q2 will be recorded and summarized for the sample to better understand how the design could scale to a larger ePCT. A preliminary efficacy analysis will utilize the total scores for the CES-D-10 (range: 0 to 30) and ZBI-6 (range: 0 to 24) calculated for all completed questionnaires. Both outcomes will be summarized at each questionnaire timepoint using means and/or medians, as appropriate. Change over the control (Q2-Q1) and intervention (Q3-Q2) periods will be calculated for each CP and summarized for the sample. Descriptive summaries will be provided for responses from CP who complete the 3-month follow-up questionnaire (Q4) within the 12-month study timeframe and before the final analytic dataset is defined. These responses will not be used in any of the formal inferential analyses.

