Analysis will utilize linear mixed-models with random effects to account for clustering of data within MBDC course section as well as repeated measures within CPs to estimate the intervention effect on depressive symptoms and care-giver burden (Equation 1). In a scaled up ePCT, we expect the unit of randomization to continue to be course section, which is reflected in our choice of random effects. The model structure will be based on a standard ANCOVA used to evaluate change that adjusts for the pre-intervention measurement of the outcome variable with the post-intervention measurement as the model outcome. Each CP will contribute a pair of data points for the control period (Pre: Q1, Post: Q2) and intervention period (Pre: Q2, Post: Q3) which requires our random effects structure to account for repeated measurements within CPs. If there is no difference in change in efficacy outcomes, we expect Q2-Q1 = Q3-Q2. Each model will include covariates to adjust for possible confounding associated with CP demographics and CP history (age, race/ethnicity, socioeconomic measures, and length of caregiving). While the relative time of measurement is considered (pre/post) our analysis does not adjust for time over the course of the study, as we hypothesize any treatment effect would be time-agnostic within the year-long pilot study time frame. When an ePCT with a longer timeline is considered, this assumption will have to be revisited. A brief assessment of self-compassion and mindfulness scales outcomes will be performed using the responses collected from the “research only” section of the questionnaires. These results will help better understand the possible mechanisms between the intervention and clinical outcome for future ePCTs. These items will be removed at the conclusion of the pilot to decrease participant burden. All analysis will be performed in SAS 9.4 and significance determined using a two-sided alpha of 0.05.

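### The pilot column of Table 2A and the 3-point power statement match a one-score-per-care-partner stepped-wedge formula, not the planned Q1/Q2/Q3 change model, so the column header is wrong for these numbers

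*Combined protocol and SAP*

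**What the plan says.** Section 9.2 states "While this pilot is not formally powered for efficacy". It then gives one power figure: "we estimate that a sample size of 120 would allow detection of a 3-point change in CES-D-10 scores associated with the intervention", with ICC 0.10, a CES-D-10 score SD of 4, 80% power and two-sided alpha 0.05. Table 2A, headed "Effect Size: Difference in CES-D-10 change between control and intervention", lists 2.68, 2.99 and 2.86 for the pilot (120 care partners (CPs), 8 courses) at ICC 0, 0.1 and 0.3. It lists 1.32, 1.49 and 1.44 for the larger trial, described as "estimates for a hypothetical ePCT with a sample size of 450 (30 courses, 15 per course". The section gives no formula, number of periods or within-CP correlation.

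The analysis is set out elsewhere. Section 9.1 says "This trial design has each individual contribute control and intervention data, allowing for within participant comparisons". Section 9.5 (Aim 2) says "Change over the control (Q2-Q1) and intervention (Q3-Q2) periods will be calculated for each CP" and "Each CP will contribute a pair of data points for the control period (Pre: Q1, Post: Q2) and intervention period", the second pair being Q2 and Q3. It also gives the null expectation: "If there is no difference in change in efficacy outcomes, we expect Q2-Q1 = Q3-Q2". The model is an ANCOVA-type mixed model for change, with the Pre score as covariate and random intercepts for CP and course. It has no study-time term. The definitions under Equation 1 set Pre to Q2 for the intervention period but print the change as Q3 - Q1.

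**The concern.** The header of Table 2A describes the contrast that section 9.5 will estimate. Two features suggest that the numbers come from another calculation. First, the pilot effect falls from 2.99 to 2.86 as the ICC rises from 0.1 to 0.3. That is typical of a stepped-wedge formula with a course intercept and period effects. Second, nothing in section 9.2 describes how repeated scores within a CP are correlated, although the planned contrast is within-CP and its precision depends on that.

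At stake is how the only stated power figure is read. Section 9.2 also says the pilot's ICC estimate will feed the power calculation of the larger trial. How an ICC acts depends on the model: a stable course intercept cancels from a within-CP contrast, whereas course differences in intervention-period change do not.

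**Working it through.** 1. Inputs. From section 9.2: N 120 in 8 courses and N 450 in 30 courses (15 per course), SD 4 (variance 16), ICC 0, 0.1 and 0.3, two-sided alpha 0.05, power 80%. The multiplier is 1.9600 + 0.8416 = 2.8016. The number of periods and the within-CP correlation are not given.

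2. Reproducing Table 2A. Take K courses, T = K + 1 periods, one course crossing at each step, and as many scores as CPs, so n = 15/9 = 1.667 per course-period (pilot) or 15/31 = 0.484 (larger trial). Let τ² = 16·ICC and σ² = 16(1 - ICC)/n. The Hussey-Hughes variance with fixed period effects is

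Kσ²(σ² + Tτ²) / [(KU - W)σ² + (U² + KTU - TW - KV)τ²].

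Here U is the number of treated course-periods, W the sum over periods of squared treated counts, and V the same sum over courses. For the pilot, U = 36 and W = V = 204, so KU - W = 288 - 204 = 84. The second bracket is 1296 + 2592 - 1836 - 1632 = 420. At ICC 0.1, σ² = 8.64 and τ² = 1.6. The variance is 8 × 8.64 × 23.04 / (725.76 + 672) = 1592.5/1397.8 = 1.139, the SE is 1.067, and 2.8016 × 1.067 = 2.990.

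| ICC | Pilot, recomputed | Pilot, stated | N=450, recomputed | N=450, stated |
|---|---|---|---|---|
| 0 | 2.679 | 2.68 | 1.316 | 1.32 |
| 0.1 | 2.990 | 2.99 | 1.495 | 1.49 |
| 0.3 | 2.857 | 2.86 | 1.444 | 1.44 |

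All six cells agree to within 0.005, and power for 3.0 points at ICC 0.10 is 80.3%. Alternatives fail for the pilot:
- no period effects: 2.05/2.12/1.94
- SD 4 read as the within-course SD: 2.68/3.15/3.41
- 15 scores per course-period: 0.89/1.11/1.00
- parallel groups with a design effect: 2.05/3.17/4.67

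3. Comparison with the planned pilot model.

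| Feature | Formula that matches | Sections 9.1 and 9.5 |
|---|---|---|
| Scores per CP | one | Q1, Q2 and Q3 |
| Pre score as covariate | no | yes |
| CP random intercept | no | yes |
| Period or study-time effects | yes | no |

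4. Planned contrast with change Q3 - Q2 and one course intercept shared by both periods. Assume 120 complete CPs and an exchangeable within-CP correlation ρ. The pre-adjusted contrast per CP is (Q3 - ρQ2) - (Q2 - ρQ1) = Q3 - (1 + ρ)Q2 + ρQ1, with variance 2(1 - ρ³) × 16. A shared course intercept has coefficient 1 - (1 + ρ) + ρ = 0 and drops out. The detectable difference is 2.8016 × √[32(1 - ρ³)/120]:
- ρ = 0: 1.45
- ρ = 0.3: 1.43
- ρ = 0.5: 1.35
- ρ = 0.7: 1.17

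Simulation of the mixed model with CP and course intercepts (1,500 runs, 8 × 15 CPs, demographic covariates omitted, ρ no smaller than the ICC) gave 1.19-1.46, 1.20-1.40 and 1.10-1.22 at ICC 0, 0.1 and 0.3. These are the empirical SD of the intervention coefficient times 2.8016.

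5. If courses also differ in intervention-period change, which Equation 1 does not include, the variance is (1 - ICC) × 32(1 - ρ³)/120 + 16·ICC/8. At ICC 0.1 and ρ = 0 this is 0.24 + 0.20 = 0.44, giving 1.86. Over ρ 0 to 0.7:
- ICC 0.1: 1.68-1.86 (normal) or 1.95-2.16 (t, 7 df, multiplier 3.2607), against 2.99 stated
- ICC 0.3: 2.38-2.48 (normal) or 2.77-2.89 (t, 7 df), against 2.86 stated

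A cruder design effect of 1 + 14·ICC gives at most 2.24 (normal) or 2.61 (t) at ICC 0.1, and at most 3.30 or 3.84 at ICC 0.3.

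6. Effect of Q3 - Q1 in Equation 1. Suppose scores fall 1 point per period with no treatment effect. With Q3 - Q2, both mean changes are -1, Pre is 1 lower in the intervention period and the Pre slope is -(1 - ρ). The fitted effect is -(1 - ρ), or -0.7 to -0.3 for ρ 0.3 to 0.7. With Q3 - Q1 and Pre = Q2, the mean changes are -1 and -2. The Pre slope is -(1 - ρ) in the control period and 0 in the intervention period, about -(1 - ρ)/2 pooled. The fitted effect is -1 - (1 - ρ)/2, or about -1.35 to -1.15. A simulation agreed (-1.1 to -1.4, against -0.3 to -0.7). The printed definition moves control-period change into the intervention effect. Q3 - Q2 reduces the shift under drift but does not remove it.

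**The case against.** The best defence is that a standard stepped-wedge approximation is reasonable planning for a declared stepped-wedge pilot, and that the table's arithmetic is sound for its implied model. Sample size was set by funding and time, the progression criteria concern attendance and recruitment diversity, and efficacy is preliminary. All of this stands and is why the point is minor. It does not rescue the header, which names a contrast that these numbers do not describe.

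A reader might infer that the whole table conflicts with the plan. The documents do not support that for the N=450 column. That trial is hypothetical, it has no fixed analysis model, and section 9.5 says that leaving out study time would need rethinking over a longer timeline. Period effects there are compatible with the text.

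A reader might also infer that Q3 - Q1 leaves the outcome undefined. It does not: the Aim 2 text gives Q3 - Q2 three ways (the change definition, the Pre/Post pair and the null expectation). The Equation 1 entry looks like a slip, but an analyst programming from it would get a different effect.

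The replacement figures are also soft, and this objection stands. The within-CP correlation is assumed. The scenarios in step 5 lie outside Equation 1. The two pre-adjusted residuals covary by -ρ²(1 - ρ), which a non-negative CP variance cannot represent. In a pooled simulation without course effects, the model SE was 0.447 against an empirical 0.494 at ρ = 0.5, with 7.6% null rejection, so true 80%-power thresholds would differ somewhat. Finally, section 9.2 mentions control means of 10 to 15 that Table 2A does not show. Part of the display may be lost, so the absence of a named method is established only for the text available.

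**Conclusion.** The point holds for the pilot column and the 3-point sentence. They match a cross-sectional stepped-wedge calculation with period effects and one score per CP. The match of six cells is strong evidence, but the method remains an inference. They are not the detectable differences of the analysis in section 9.5. For that analysis, with Q3 - Q2 and a shared course intercept, the figure is about 1.2 to 1.5 points under the assumptions in step 4, roughly half or less of the 2.99 stated at ICC 0.10.

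A reader might infer that the pilot is under-powered, or that the table is safely conservative throughout. Neither is supported. At ICC 0.10 every scenario examined falls below 3 points. At ICC 0.3 the result depends on how course variation enters, and some scenarios reach or exceed 2.86. The magnitudes are illustrative. Severity is minor, because efficacy is not formally powered and no enrolment or progression decision rests on the table.

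**What to change.** 1. In Equation 1, change the intervention-period definition from Q3 - Q1 to Q3 - Q2, in line with the Aim 2 text.
2. Then do one of the following:
   - recompute the pilot column and the 3-point sentence for the planned model over a stated range of within-CP correlation, saying how course variation enters and using a small-cluster t reference only where it affects the contrast; or
   - keep the figures, state that they are a cross-sectional stepped-wedge approximation with period effects and one score per CP, and correct the Table 2A header.
3. For the N=450 column, state the method and whether period effects and repeated measures are assumed.

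The cost is a one-term correction plus either a label and header edit or a short recalculation in section 9.2. Enrolment and conduct do not change.
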